6.1.2 Per-Protocol (PP) Population

The Per-Protocol population will consist of all subjects who complete the primary endpoint information without a major protocol deviation; determination of protocol deviation severity will follow Sponsor procedure, CAP-0017. PP will include subjects who have evaluable CTs both at baseline and at 30-day follow-up. The PP population analyses will be completed based on the randomized treatment arm. The PP population may be used for all effectiveness analyses as sensitivity analyses with groups based on the randomized treatment.

The definition of major protocol deviations is defined in CAP-0017. The list of deviations will be reviewed, and deviations that will exclude subjects from the PP population will be identified and documented in an Excel file that will be approved by the Sponsor. The approved Excel file will be incorporated into analysis programming and used to exclude subjects from the PP population. Subjects who are screened but not randomized will not be included in analysis. Subjects who were randomized but failed screening intraoperatively will not be included in the analysis. Any information on these subjects will be made available in a listing if requested by the IRB or FDA.

6.1.3 Safety Population

The Safety population consists of all subjects who had a procedure performed. The Safety population will be used for the safety summaries (AEs) with groups based on the actual treatment received.

6.2 **PATIENT DISPOSITION**

The number of subjects included in each analysis population (ITT, Safety, and PP) will be summarized by treatment group and overall for all randomized subjects. The number of subjects screened, enrolled, randomized, randomized and not treated, completed the study, and discontinued the study early (including the reasons for discontinuation such as randomized and not treated due to a screen failure) will be summarized for each treatment group and overall.

Subjects who are excluded from an analysis population will be summarized by the reasons for exclusion by treatment group and overall.

6.3 SUBJECT ACCOUNTABILITY

At each post-treatment visit, the number of subjects who should theoretically be included, the number of deaths, the number of subjects not yet overdue, the expected number of subjects, the number of subjects with actual data, and percent follow-up will be summarized by count only.

A subject will be considered theoretically included at a given visit if they satisfy the following:

data extraction date - index procedure date > visit date

Where, data extraction date = date of the data extract used for generation of tables, listings, and figures (TLFs)

index procedure date = date of procedure

visit date = date of visit for which the relevant study day is needed

The number of deaths at each visit is given where the date of death is on or before the upper protocol-specified window limit for a given visit. The number of deaths is cumulative.

A subject will be considered not yet overdue if they have not been evaluated at a given visit, has not experienced death, and the number of days between the data extraction date and the index procedure falls within the upper half of the time window period.

The expected number of subjects is given by subtracting the number of deaths and not yet overdue from the number of subjects that should be theoretically included at a given visit.

A subject will be counted as actual if they have any data available at the given visit.

Percent follow-up is calculated as (Actual/Expected)*100.

6.4 **DEMOGRAPHIC AND BASELINE CHARACTERISTICS**

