6. STUDY ENDPOINTS

6.1. Primary Safety Endpoint

The rate of occurrence of each arm of clinically significant serious adverse events defined as:

- Serious infection (urosepsis, pyelonephritis) requiring hospitalization and treatment through 90 days post index procedure
- New urinary tract stricture formation requiring surgical intervention through 90 days post index procedure

Confidence intervals will be presented to aid in the evaluation of the incidence of clinically significant serious adverse events, both for each treatment group individually, and for the difference in the rates between the two treatment groups.

6.2. Primary Efficacy Endpoint

Treatment success: Proportion of study subjects who have a complete absence of stone(s), or have residual fragments measuring to ≤ 2 mm, as assessed by CT imaging through 30 days follow-up post index procedure. CT imaging will be assessed by an independent core lab to determine treatment success. Treatment success, as defined by an absence of residual fragments >2mm on any dimension, has been identified as a priority in stone care in recent publications including Margaret Pearle's widely cited "Is Ureteroscopy as Good as We Think", published in the Journal of Urology in 2016 [12]. Increasing awareness and clinical prioritization of residual fragments in ureteroscopic laser lithotripsy derives in large part from expanded use of CT follow-up imaging in stone subjects. CT imaging has allowed characterization of residual fragments and full appreciation of their clinical significance, with rigorous studies of residual fragment natural history having established a 2mm threshold as a critical size above which additional stone events are particularly frequent [22], [23]. Therefore, the primary efficacy endpoint will demonstrate that the investigational arm (Acoustic Enhancer +_URS-LL) is superior in the fragmentation of stones to $\leq 2mm$ versus the control arm (URS-LL).

6.3. Secondary Efficacy Endpoint

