8.5. 30-day follow-up (30 +14 days after procedure)

- Conduct focused urogenital calculus physical exam and vital signs.
- Measure serum creatinine to assess renal function.
- Document any reported AEs since last visit (see Adverse Events section below)
- If symptoms of Urinary Tract Infection (UTI) are reported by subjects, conduct a urinalysis and subsequent urine culture if clinically indicated to verify presence/absence of UTI.
- Document all prescription medications. In addition, document any non-prescription medication that may impact stone disease, acting as stone formation promoters (e.g., calcium or ascorbic acid) or stone formation inhibitors (e.g., magnesium or citric acid)
- Conduct CT imaging following acquisition parameters delineated in CLIN-0002: Image Acquisition Protocol, AEROLITH Study
 - **Note 1:** As presence of ureteral stents may obscure image analysis, remove stents from the treated kidney/ureter prior to collecting the CT images.
 - **Note 2:** If a stent is removed outside of the window (3-14 days post procedure), this will be captured and documented using Protocol Deviation CRF as minor protocol deviation.
 - Note 3: If a stent is removed at >14 days, verify absence or presence of calcification and/or encrustation via standard of care imaging (e.g., KUB X-ray). If calcification and/or encrustation is observed, complete Adverse Event CRF.
- Upload the CT images to the core lab for analysis.
- Complete Study Exit CRF
 - **Note 1:** For those subjects with new or on-going device and/or procedure-related serious adverse events at 30 days post procedure, they will be followed until the event has resolved or is deemed stable by the investigator.
 - **Note 2:** For those subjects with new or on-going device and/or procedure related hydronephrosis and those subjects with pre-existing (prior to treatment) hydronephrosis that have worsened or recurred since baseline, they will be followed through 90-days post procedure (see below).

8.6. 90-day follow-up and Study exit (90 +/- 21 days after last treatment) only for those subjects with new and unresolved device and/or procedure related hydronephrosis and subjects with pre-existing (prior to treatment) hydronephrosis that have worsened or recurred at 30 days

- Conduct focused urogenital calculus physical exam and vital signs.
- Document any reported AEs since last visit (see Adverse Events section below).

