2 STUDY DESIGN AND PROCEDURES

The clinical study is a prospective, multicenter, two-arm, randomized, double blinded study in male or female subjects 18 to 75 years of age with a diagnosis of urinary stone disease. For this study, double blinded means: 1) study subjects will not be informed of their treatment allocation through the index procedure, and 2) in assessing stone fragmentation using a CT image as defined in the primary endpoint, an independent radiologist will conduct the assessment and will be blinded to the treatment allocation of each subject's CT image.

The study visits consist of Screening, Treatment/Procedure [Day 1], Day 14 (+/- 4 days), Day 30 (+14 days), and Day 90 (+/- 21 days). Subjects who have unresolved hydronephrosis at Day 30 need to continue to Day 90. At 90-days post procedure, subjects who have on-going device and/or procedure-related serious adverse events (including device and/or procedure related hydronephrosis) and subjects with pre-existing (prior to treatment) hydronephrosis that have worsened or recurred will continue to be followed until the event has resolved or is deemed stable by the investigator prior to study exit. A total of 196 subjects will be enrolled in this study at up to 27 investigational sites located in the U.S., with each site enrolling no more than 20% of the total.

Following consent and if a subject meets the study's inclusion/exclusion criteria, the subject will be randomly assigned to the investigational arm (Acoustic Enhancer with URS-LL) or

control arm (URS-LL) on the day of the procedure. Random assignment will be conducted using an allocation ratio of 1:1 with one subject randomized to the investigational arm for each subject randomized to the control arm. A minimum of 176 evaluable subjects will be needed for analysis. After randomization and during procedure, eligibility criteria will be verified. If subjects are found to not meet eligibility criteria they will be considered screen failures and will not be considered randomized and treated for analysis purposes.

Random assignment will be conducted using a stratified permuted block design generated separately for each clinical site.

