13 CHANGES TO THE ANALYSES PLANNED IN THE PROTOCOL

In the protocol it is stated that the total number of secondary stone treatments will be summarized and a Cochran-Armitage trend test will be used to evaluate the null hypothesis that there is no trend in the number of stones between the groups. This was removed from the SAP. Because subjects exit the study 30 days after receiving treatment, this data is unlikely to be available.

No further changes exist between the protocol-defined statistical analyses and those presented in this statistical plan.

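### SAP 6.3 counts subjects who are not due at Day 90 as expected there, so the Day 90 percent follow-up mixes the share due with completeness among those due (minor, descriptive only)

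*SAP*

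**What the plan says.** SAP 6.3 covers each post-treatment visit with the same steps, and SAP 2 lists Day 90 among the visits.

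- **Theoretically included:** the subject satisfies "data extraction date - index procedure date > visit date".
- **Expected:** obtained by "subtracting the number of deaths and not yet overdue from the number of subjects that should be theoretically included at a given visit".
- **Actual:** any subject with any data at the visit.
- **Result:** "Percent follow-up is calculated as (Actual/Expected)*100".

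The output is Table 14.0.3, on the ITT population.

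Day 90 is a conditional visit. The heading of Protocol 8.6 restricts it, as judged at Day 30, to patients "with new and unresolved device and/or procedure related hydronephrosis and subjects with pre-existing (prior to treatment) hydronephrosis that have worsened or recurred". The footnote to Protocol Table 2 also confines it to subjects with hydronephrosis. SAP 2 has a shorter statement: "Subjects who have unresolved hydronephrosis at Day 30 need to continue to Day 90". SAP 13 describes everyone else when it drops an analysis of secondary stone treatments: "Because subjects exit the study 30 days after receiving treatment, this data is unlikely to be available".

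**The concern.** A percent follow-up is read as completeness: of the subjects who should have come, how many came. At Day 14 and Day 30 the rule gives that, because every treated subject is scheduled. At Day 90 the same rule places in the denominator subjects who left at Day 30 exactly as planned. SAP 6.3 has no Day 90 condition and does not point to the sentence in SAP 2 that would supply one.

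What is at stake is one line of a descriptive table, but that line has a purpose. Subjects due at Day 90 have unresolved, worsened or recurred hydronephrosis, and the visit gives them a renal-bladder ultrasound. Whether they returned is what the row should show. A figure of 5% to 10% could be taken for heavy loss to follow-up when there was none, or could hide real non-attendance in a small group.

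**Working it through.** **Inputs from the documents.** There are 196 randomized subjects (SAP 3). The Day 90 window is ±21 days (SAP 2), so it closes at Day 90 + 21 = 111. The accountability steps are those of SAP 6.3.

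**Inputs assumed.** Neither document gives the share of subjects due at Day 90 or their attendance. The share due is varied from 2% to 30%. Only subjects who are due are taken to have Day 90 data.

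**The plan's own figure.** No Day 90 percentage is stated, so there is none to reproduce. The sample size used as the illustrative total does reproduce: 88 per arm gives 176, and 176 / (1 − 0.10) = 195.6, rounded up to 196.

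**Reading the rule.** The inclusion step sets a number of elapsed days against a visit date, so its units do not match. The workable reading is the target study day (14, 30 or 90). SAP 6.3 supports this: its not-yet-overdue category consists of subjects who have not been evaluated, so inclusion cannot depend on the date of a visit that took place.

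**Formula.** Let T be the number past the Day 90 time point, D deaths, Y not yet overdue, q the share due, and c completeness among those due. Then

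printed percent = 100 × q × c × T / (T − D − Y).

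Once every subject is past Day 111, Y = 0. With D = 0 the expression reduces to 100 × q × c. Since c is at most 1, the printed figure cannot exceed 100 × q.

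**Results with T = 196, D = 0, Y = 0.**

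| Due | Attending | Completeness among those due | Printed under SAP 6.3 |
|---|---|---|---|
| 20 | 20 | 20/20 = 100% | 20/196 = 10.2% |
| 20 | 15 | 15/20 = 75% | 15/196 = 7.7% |
| 15 | 15 | 15/15 = 100% | 15/196 = 7.7% |
| 20 | 10 | 10/20 = 50% | 10/196 = 5.1% |
| 10 | 10 | 10/10 = 100% | 10/196 = 5.1% |

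Rows two and three print the same figure for different completeness, and so do rows four and five. The percentage alone therefore cannot identify completeness.

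**Range over the assumed share due, with full attendance.** 2% (4 due): 4/196 = 2.0%. 5% (10 due): 5.1%. 10% (20 due): 10.2%. 20% (39 due): 39/196 = 19.9%. 30% (59 due): 59/196 = 30.1%. Completeness is 100% in every case.

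**Sensitivity.** Two deaths move the first row only to 20/194 = 10.3%. With a total of 176 and 18 due, full attendance prints 18/176 = 10.2%.

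**The case against.** The strongest reply is that this is an ambiguity and not a wrong denominator. SAP 6.3 speaks of subjects who should be included, SAP 2 says who continues to Day 90, and SAP 1 sends the reader to the protocol for operational detail. A programmer who read everything could restrict the row. That is possible, but SAP 6.3 gives an explicit formula, and the formula does not do so. The sentence in SAP 2 also omits the conditions in Protocol 8.6 (device or procedure relatedness, or worsening or recurrence of pre-existing hydronephrosis), so two careful programmers could count different subjects as due. The SAP 2 wording matches the protocol synopsis and the Table 2 footnote, so the SAP did not create that difference. Harmonizing the protocol is a separate matter.

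A second reply is that non-return would be seen elsewhere. Protocol 7.6 ties loss to follow-up to the last scheduled visit, including Day 90 for subjects with unresolved hydronephrosis. SAP 6.2 tabulates early discontinuations with reasons, Listing 16.2.1.2 lists them, and SAP 6.5 has a study-visit deviation category. This stands in part: a subject who was due and then lost should appear in those outputs. It would be wrong to infer that such losses would be invisible. None of those outputs prints the number due, however, so none replaces a correct row.

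Third, the actual and expected counts are printed beside the percentage, so a reader could see that the denominator is large. That also stands, but the number due still could not be recovered from them.

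**Conclusion.** The rule is wrong as written for Day 90, and the consequence is minor. At final extraction the printed percentage is about the share due multiplied by completeness. Its exact size depends on a share due that the documents do not give; its ceiling at about the share due does not. The result rests on the target-day reading, on closed windows, and on Day 90 data coming only from subjects who are due. The total of 196 is an upper case, because randomized subjects later found ineligible leave the ITT population; the percentages change little at 176.

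Three stronger readings are not supported. The expected count is not set by elapsed time alone, since deaths and not-yet-overdue subjects are subtracted. The percentage is not a pure measure of the share due, since completeness also moves it. Nor does the defect reach the trial's conclusions: no endpoint, analysis population, success criterion, alpha or power uses this row, and the Day 14 and Day 30 rows lack the problem. The primary safety endpoint does run to 90 days (its first component is "Serious infection (urosepsis, pyelonephritis) requiring hospitalization and treatment through 90 days post index procedure"), but whether 90-day events are adequately ascertained is a separate question that this row neither causes nor settles.

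**What to change.** In SAP 6.3, before database lock:

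1. Replace the visit date in the inclusion rule with the target study day: 14, 30 or 90.
2. For Day 90, compute the theoretical count, the expected count and percent follow-up only among subjects who meet the criterion of Protocol 8.5 Note 2 and 8.6 at Day 30. Name that criterion in the text.
3. In the Day 90 part of Table 14.0.3, print the number due beside the total number of ITT subjects.

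Step 3 is needed because a restricted denominator alone would hide how few subjects are observed at Day 90. In the example with 15 attending, 196 − 15 = 181 subjects (92.3%) have no Day 90 data. The planned actual count already gives the number with data, so no further row is required.

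The cost is a sentence or two in the SAP, one programming condition and one added count in an existing table. Who returns does not change, and no protocol amendment is needed.

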6.4.1 Demographic and Baseline Characteristics

Demographic variables will include age, sex, race, and ethnicity. Baseline characteristics include height (cm), weight (kg), and body mass index (BMI; kg/m²). Demographics and baseline characteristics will be presented in a by-subject listing and summarized overall and by treatment group using the ITT, PP and Safety populations.

6.4.2 Baseline Disease Status/Disease History

Disease history information will be collected on the Urinary Stone History form, which include:

- History of treatment procedures in study/treatment side (Yes/No)
- Existence of stent in place and whether the stent appears calcified or encrusted is in place
- Existence of radiolucent stones on KUB or Scout CT Imaging and the imaging modality used to access radiolucent stones if radiolucent stones are present

Disease status information will be collected on the Vital Signs/Physical Exam form and the Stone Location and Measurement form, which includes:

- Conduct of focused urogenital calculus physical exam and abnormality if conducted (Abnormal findings/No abnormal findings)
- Location of each stone (investigator reported)
- Largest diameter (mm) of each stone (investigator reported)
- Cumulative diameter (mm) of all stones (investigator reported)

Urinary stone history and stone location and measurement will be presented in separate bysubject listings and summarized together overall and by treatment group using the ITT, PP and Safety populations.

6.4.3 Medical and Procedural History

Medical and procedural history will be collected at screening for each body system. All medical history will be presented in a by-subject listing.

6.4.4 Prior and Concomitant Medications

Prior medications are those that stop prior to the start of URS-LL with Acoustic Enhancer URS-LL control procedure. Any medication that stops at or after this time or with missing stop dates is considered concomitant medication.

Prior and concomitant medications are collected throughout the study. Prior and concomitant medications will be coded using World Health Organization Drug Dictionary Anatomical Therapeutic Chemical (WHO/ATC) classification index version Global B3, ATC Level 2. The number and percentage of subjects who take prior and concomitant medications will be summarized separately by drug class and preferred term, overall and by treatment group, for the safety population. A separate summarized by timing (prior to treatment, post-treatment, at Day 14, at Day 30), drug class and preferred term, overall and by treatment group, for the safety population.

A separate summary will also be provided for medications of interest. These will include, but are not limited to, prescription medications associated with kidney stones, post operative

pain medications and medications for AEs. ARA will provide a medication list to Applaud and Applaud will identify these medications.

All medications captured in CRFs will appear in by-subject data listings.

6.5 **PROTOCOL DEVIATIONS**

Protocol deviations will be captured on CRFs and additional tracked by the operational study team members. They will be categorized as Informed Consent, Inclusion/Exclusion, Study Visit, Clinical Exam/Assessment, or Other. Major protocol deviations are defined in Sponsor's CAP-0017 and will be determined by Sponsor's study team prior to final analysis and unblinding. Subjects experiencing a major protocol deviation will be excluded from the PP population during analysis.

Protocol deviations will be summarized as the number of subjects with any protocol deviation, protocol deviations by category and major/minor status within category, overall and by treatment group for the ITT population.

7 STUDY PROCEDURE MEASUREMENTS

The following Investigational Device/Unblinded Procedure Details will be summarized overall and by treatment group for the ITT population:

- Treatment Side
- Anesthesia Used
- Were the Laser Pulse Energy settings used throughout the procedure within 0.2 and 1.5 J
- Were the Laser Pulse Repetition Rates used throughout the procedure within 5 Hz to 60 Hz?,
- Did the time-averaged power (defined as the product of the Laser Pulse Energy and the Laser Pulse Repetition Rate) exceed 25 W during any portion of the procedure?,
- Were continuous suction devices (e.g., ClearPetra, LithAssist) Used?,
- Post-Procedure Ureteral Stent
- Was the URS-LL procedure able to be performed
- Did the subject remain blinded to the treatment assignment through procedure?,
- Overnight hospital stay required (>24 hours)?
- Duration of fibre placement (min)
- Total Lasering Time (min)

All procedure details will be provided in three by-subject listings to account for all data collected. Pregnancy tests will also be provided in a by-subject listing.

